2.5 Safety Analysis

All safety data will be summarized descriptively by treatment group based on the safety population using the OC. There are no planned inferential statistical analyses of safety endpoints.

2.5.1 Extent of Exposure

Because subjects will receive a single dose of investigational product, no summary of extent of exposure will be performed. Extent of exposure will be provided in a subject data listing.

2.5.2 Adverse Events

An overall summary of all AEs will be provided by treatment group, which will include:

- number and percentage of subjects with at least one AE and number of events,
- number and percentage of subjects with at least one TEAE and number of events,
- number and percentage of subjects with at least one related TEAE and number of events,

GALDERMA
Title
43USD1804 Statistical analysis plan

- number and percentage of subjects with at least one mild, moderate, and severe TEAE and number of events,
- number and percentage of subjects with at least one TEAE leading to discontinuation and number of events,
- number and percentage of subjects with at least one serious TEAE and number of events.

All TEAEs, serious TEAEs, TEAEs by maximum intensity, TEAEs by causality, TEAEs by maximum intensity and causality, related TEAEs, and TEAEs leading to discontinuation will be summarized by treatment group, SOC, and PT including number of subjects with at least one event, percentages, and number of events.

For related AEs, the number of days to onset and duration of event will be summarized by treatment group, SOC, and PT.

Time to onset of an AE will be derived as the start date minus the date of treatment. If the start date is missing, it will be assumed that the AE started on the day of treatment.

Duration of an AE will be derived as the stop date minus the start date + 1. If the start date is missing, it will be assumed that the AE started on the day of treatment. Missing stop date will not be imputed and therefore no duration will be calculated in these cases.

For subject counts, a subject will only be counted once per SOC and once per PT in cases where multiple events are reported for a subject within SOC or PT. For event counts, subjects with multiple events in a category will be counted for each event.

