7.2.5.2 Reporting Procedures

7.2.5.2.1 Procedure for Reporting Adverse Events

The collection of AEs is from the time that a subject signs the ICF to their final visit.

At each post-enrollment visit, the Investigator (or sub-Investigator) will question the subject about AEs using an open non-persuasive question to elicit reporting of AEs, for example “Have you noticed any change in your health since the last visit?” Directed questioning and examination will then be performed as appropriate.

Any AE occurring during the AE reporting period, whether it is related to the study product or not, will be recorded immediately in the source document, and described on the AE form of the eCRF along with the date of onset, severity, relationship to the study product, action taken and outcome, without omitting any requested and known information. Additional information may be requested under certain circumstances.

Adverse Events (AEs) assessed as related to the treatment or study procedure will be monitored until they have resolved or reached a stable condition. Other AEs will be monitored until the last visit if they have not resolved or reached a stable condition.

The Investigator will obtain and maintain in the subject’s files all pertinent medical records, information and medical judgment from colleagues who assisted in the treatment and follow-up of the subject. If necessary, the Investigator will contact the subject’s personal physician or hospital staff to obtain further details.

For SAEs (see Section 7.2.5.2.3) and pregnancies (see Section 7.2.5.2.4), the Sponsor is to be informed immediately. The event must be reported by e-mail to the Safety email within 24 hours of receipt of the information (contact details in Section 7.2.5.2.3).

7.2.5.2.2 Procedure for Reporting an Adverse Event that may indicate remote spread of toxin effect or a hypersensitivity reaction

Adverse events that may indicate remote spread of toxin or hypersensitivity reactions (Appendix 6) should be reported to the Safety email [redacted] within 24 hours of awareness using the AE Clarification Form.

Effective date: 2019-08-09 13:21

In case of difficulty to obtain all the required information within 24 hours, an initial report can be submitted with follow up information provided within 24 hours of awareness of the new information.

The following information should be provided on the AE Clarification Form:

- Subject identification (subject number and initials)

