1.6 Safety Endpoints

Safety endpoints include:

(i) Treatment Emergent Adverse Events (TEAEs)

Adverse events (AEs) are to be monitored throughout the course of the study. The study period for the purpose of AE collection is defined as the period from the signing of a study specific informed consent to study exit for a subject. AEs recorded on the electronic case report forms (eCRFs) will be coded using the Medical Dictionary for Regulatory Activities (MedDRA). AEs will be classified as treatment-emergent adverse events (TEAEs) if the AE had an onset time greater than or equal to the time of the dose of study treatment.

Adverse events endpoints include:

- Incidence,
- Causality (related/not related to investigational product or protocol procedure),
- Intensity (mild/moderate/severe),
- Time to onset,
- Duration,
- Leading to study withdrawal,
- Seriousness.

(ii) Focused Physical Examination

At all visits the Investigator or designee will perform a physical examination of the subject that includes the face, head, and neck. The Investigator may choose to investigate any other sign that he/she observes during the physical examination and should assess all abnormal findings for clinical significance.

(iii) Vital Signs

Vital signs (including blood pressure, heart rate, and respiratory rate) will be evaluated at the baseline visit (pre and post-treatment), and at each study visit thereafter through the termination visit.

Vital signs endpoints include:

- Values,
- Changes from baseline.

All abnormal values at the screening visit identified as clinically significant by the Investigator will be recorded in the medical history.

For any clinically significant changes from the screening visit, an AE is to be recorded.

Normal ranges checks, as programmed in the eCRF to alert the investigator to assess clinical significance for values outside of these ranges, are shown in Table 4 below.

Title
43USD1804 Statistical analysis plan Doc id GALDERMA

Table 4. Vital Sign Normal Ranges

Measure	Normal Range
Sitting Systolic blood pressure	90-150 mmHg
Sitting Diastolic blood pressure	60-90 mmHg
Sitting Heart rate	50-100 beats/min
Sitting Respiratory rate	12-24 breaths/min

(iv) **Jawline and Oral Commissure Safety Assessment**

To determine if treatment with abobotulinumtoxinA or placebo of the platysmal bands adversely affects the subject's jawline or oral commissures, the Investigator will assess these areas relative to the subject's pre-treatment appearance

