2.5.3 Other Safety Assessments

Data for vital signs will be summarized by treatment group using descriptive statistics with the value at each visit as well as the change from baseline. The numbers and percentages of subjects with abnormalities in focused physical examination and for the safety assessment of jawline and oral commissures will also be summarized by treatment group. The results of the urine pregnancy tests will only be listed.

[figure not shown]
AEs of special interest (AESIs) for abobotulinumtoxinA are TEAEs that suggest a possible remote spread of effect of the toxin or events suggestive of hypersensitivity like reactions. TEAEs due to possible remote spread of the effects of abobotulinumtoxinA will be identified using the list of MedDRA PTs compatible with the mechanism of action of BoNT-A and based on the recommendations from the Committee for Medicinal Products for Human Use (CHMP) and the FDA. TEAEs potentially representing hypersensitivity reactions will be identified using the Standardised MedDRA Query (SMQ) (narrow search query) for hypersensitivity reactions. A list of adverse events potentially suggestive of remote spread of toxin is in Section 5 Appendix A. A list of MedDRA PTs in the hypersensitivity SMQ is in Section 6 Appendix B.

All TEAEs identified using the search strategy described above will be medically evaluated during the study, before the database lock and unblinding, by the sponsor to identify events which could possibly represent "remote spread of effect of toxin", or which are suggestive of "hypersensitivity reactions" due to study treatment administration. Cases will be excluded if they are confounded by presence of alternative clinical etiologies (medical history, concomitant medication or diagnosis which could account for the symptoms); if they are considered to be local effects instead of distant spread as judged by the site of injection; the time period between study treatment administration and event onset is not in accordance with the expected mechanism of action; or due to insufficient information/evidence to make an assessment.

Doc id 43USD1804 Statistical analysis plan -🖧 GALDERMA

In the tables and listings, only the final list of AESIs confirmed by the sponsor as "a possible remote spread event" or "hypersensitivity reactions" will be taken into account.

Data Safety Monitoring Committee Reviews

Pre-Specified Stopping Criteria 2.6.1

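### Setting a missing AE start date to the day of treatment gives false time-to-onset and duration values in the related-AE summaries

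*SAP*

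**What the plan says.** SAP 2.5.2 defines the two timing variables. Onset: "Time to onset of an AE will be derived as the start date minus the date of treatment". Duration: "Duration of an AE will be derived as the stop date minus the start date + 1". After each definition it adds the same sentence: "If the start date is missing, it will be assumed that the AE started on the day of treatment". A missing stop date is handled the other way: "Missing stop date will not be imputed and therefore no duration will be calculated in these cases".

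The outputs are set in the same section: "For related AEs, the number of days to onset and duration of event will be summarized by treatment group, SOC, and PT". SAP 1.6 lists time to onset and duration among the adverse event endpoints, and Protocol 9.1.3.1 also promises them for related events.

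SAP 2.4.2 and 2.5 put the safety analyses on an observed-cases basis. SAP 2.4.1, writing about efficacy summaries, explains observed cases as data without imputation. SAP 2.5 plans no inference on safety.

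**The concern.** A Day 0 assumption is a familiar cautious default when the question is whether an event counts as treatment-emergent. Here, though, it is written into the derivation of two timing variables. Day 0 is then a specific value, and it is false for any event that began later. The error has a fixed direction: onset can only be too early and duration only too long.

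At stake is the description of when related events begin and how long they last in a dose-ranging toxin study. Each dose has about 60 subjects, so a table by SOC and PT may have cells with only a few events, where one artificial value can dominate.

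**Working it through.** The documents state no onset, duration or missingness figure, so there is nothing to reproduce. The check applies the SAP's formulas directly.

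**Inputs.** From SAP 2.5.2: onset = start − treatment; duration = stop − start + 1; missing start = treatment day (Day 0); missing stop = no duration. Assumed, because not in the documents: true onset day s, true duration d, and fraction f of related events without a start date. Stop dates are taken as known, and missingness as unrelated to timing.

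**One event.** The stop day is s + d − 1.

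- True values: onset s; duration (s + d − 1) − s + 1 = d.
- Under the rule: onset 0 − 0 = 0, error −s; duration (s + d − 1) − 0 + 1 = d + s, error +s.

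| Event | True onset / duration | Reported onset / duration |
|---|---|---|
| Day 35 to Day 40 | 35 / 40 − 35 + 1 = 6 | 0 / 40 − 0 + 1 = 41 |
| s = 14, d = 14 | 14 / 14 | 0 / 28 |
| s = 30, d = 7 | 30 / 7 | 0 / 37 |
| s = 0, any d | 0 / d | 0 / d (no error) |

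If the stop date is missing too, onset is still set to 0 but no duration is produced.

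**Mean over many events.** Mean onset = s(1 − f); mean duration = d + f·s. With d = 14, the cells show mean onset / mean duration:

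| f | s = 7 | s = 14 | s = 30 |
|---|---|---|---|
| 0% | 7 / 14 | 14 / 14 | 30 / 14 |
| 1% | 6.93 / 14.07 | 13.86 / 14.14 | 29.7 / 14.3 |
| 5% | 6.65 / 14.35 | 13.3 / 14.7 | 28.5 / 15.5 |
| 20% | 5.6 / 15.4 | 11.2 / 16.8 | 24.0 / 20.0 |

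**Small SOC/PT cell.** With k events, one start date missing and s = d = 14, mean onset = 14(k − 1)/k and mean duration = 14 + 14/k:

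| k | Mean onset | Mean duration |
|---|---|---|
| 1 | 0 | 28 |
| 2 | 7 | 21 |
| 5 | 11.2 | 16.8 |
| 10 | 12.6 | 15.4 |

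The correct values are 14 and 14 throughout. SAP 2.1.2 also reports the minimum, and one missing start date is enough to make the minimum onset in a cell 0.

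**Consistency.** Duration needs both dates and is equally unknown if either is absent. The SAP gives no duration when the stop date is missing, yet produces one when the start date is missing. The second treatment is also hard to square with an observed-cases basis for safety.

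**The case against.** **Missing start dates should be rare.** The protocol asks for each event to be "described on the AE form of the eCRF along with the date of onset, severity, relationship to the study product", and Protocol 10.3 describes computerised and manual data checks. This stands. It limits the likely size but does not make the rule correct when a date is missing.

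**The rule is pre-specified, equal across arms, and overstates duration, which errs against the product.** The first part is true. But a common rule gives a common error only if the missing fraction and the true onset times are alike across arms. A bias against the product is still a bias in a descriptive timing table, and the onset error comes with it.

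**The consequence is small.** This stands. Safety is descriptive, and listings show the eCRF data beside the derived variables, so an imputed date can be traced.

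Three stronger readings are tempting, and the documents do not support them.

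- *Real toxin-spread cases could be dropped from the AESI list.* SAP 2.5.3 does exclude cases where "the time period between study treatment administration and event onset is not in accordance with the expected mechanism of action". But that is a medical evaluation by the sponsor during the study, and nothing says that an imputed date enters it. Protocol 7.2.5.2.2 collects the onset date and time of such events on a separate form. A case with unknown onset could also be excluded for insufficient information, whatever the imputation.
- *Negative durations could reach the tables.* The AE collection period is "defined as the period from the signing of a study specific informed consent to study exit for a subject", so an event that ended on Day −3 with no start date would get −3 − 0 + 1 = −2 days. But the planned summaries cover related events only. Under Protocol 7.2.5.1.7, related means possibly caused by the product or its injection, and an event that ended before injection cannot properly qualify. At most the value could appear in a listing.
- *A known month or year is ignored.* The sentence speaks of a missing date. Only the heading of SAP 2.1.3, on data transformations, can be read, so the absence of a partial-date rule cannot be asserted.

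**Conclusion.** The point holds as a small error in a descriptive output. For a related event that began after the day of treatment and has no start date, the rule makes onset too early by the true treatment-to-onset interval. It makes duration too long by the same amount if the stop date is known. Under the assumed values, the shift in an overall mean is under one day at 5% missing with a 14-day onset, and 6 days at 20% missing with a 30-day onset. A cell with one or two events can be dominated by a single imputed date. The actual size depends on a missing rate that the documents do not give, and it is nil at 0%. No efficacy or inferential result is affected. The inconsistency with the stop-date rule and with the observed-cases basis exists whatever the rate.

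**What to change.** Amend SAP 2.5.2, which SAP 2.1 allows before database lock:

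1. Use the Day 0 assumption only to classify an event as treatment-emergent, and not where the stop date precedes treatment.
2. When the start date is fully missing, leave time to onset and duration missing, and report the number of such events by treatment group. This matches what is already done for missing stop dates.

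The cost is about two sentences and a small programming change. The downside is that a few events drop out of the two summaries. If events without a start date differ in timing from the rest, the observed summaries would not represent them, which is why the count should be reported.

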- Event description including observed symptoms
- Medical history related to event
- Event onset date and time
- Depth of injections
- Interventions implemented to treat event
- Event outcome (with resolution date and time if applicable)
- Relatedness to study product or procedure
- Seriousness of event
- Study treatment information (number of injections, date of injections, name of product injected, volume injected, etc.)

If the Investigator assesses the AE as serious, an SAE report should be submitted as specified in section 7.2.5.2.3.

Upon receipt of the AE Clarification Form, the Medical Monitor and Sponsor will review the information, assess the event, and report to the IRB and RA as applicable.

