9.1.3.1 Safety Analysis

AEs will be summarized descriptively by treatment group, SOC and PT using number and percentage of subjects with at least one event and number of events. The results will be further broken down by other factors such as severity, causality, seriousness, and whether the event led to discontinuation, and action taken for the event. Duration and time to onset of related AEs will also be presented by treatment group, SOC and PT.

The numbers and percentages of subjects with abnormalities in physical examination will also be summarized, as well as vital signs and safety assessment of jawline and oral commissures. The results of the urine pregnancy tests will be listed.

All AEs will be monitored by the Sponsor to determine if they meet the criteria of remote spread of effect of the toxin or hypersensitivity. A list of preferred terms for these types of events will be provided in the SAP, and will be further analyzed to determine if there is a plausible possibility that they represent distant spread of toxin or hypersensitivity. In order to perform the analysis, variables including alternative etiology (medical history, concomitant medication, or diagnosis which could account for the symptoms), location of Dysport administration, and temporal relationship to Dysport administration will be considered by the Sponsor.

Effective

Version: 6.0

Effective date: 2019-08-09 13:21

Effective

Version: 6.0

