2.1.2 Reporting Conventions

The formats for the tables, listings, and figures described in this SAP will be provided in a companion document. Changes to the formats of these reports that are decided after the finalization of the SAP will not require an amendment. In addition, any additional supportive or exploratory analyses requested after SAP approval will not require amendment of the SAP. These additional analyses will be described in the CSR.

All study data from the eCRFs as well as derived variables will be provided in subject data listings. An indication of specific listings for each data type will not be indicated in the text of subsequent SAP sections. Data listings supplied as part of the CSR will be sorted by treatment group, study center number concatenated with subject number, assessment dates, and/or time point.

The following conventions will be applied to all data presentations and analyses:

- Placebo-treated subjects will be pooled together in summary tables and for analyses.
- Treatment groups to be summarized include abobotulinumtoxinA and pooled placebo.
- Quantitative variables will generally be summarized by the number of subjects, mean, standard deviation, median, minimum, and maximum. Unless otherwise specified, the minimum and maximum values will be displayed to the same number of decimal places as the raw data, the mean and median will be presented to one extra decimal place compared to

GALDERMA

Title

43USD1804 Statistical analysis plan -

the raw data, and the standard deviation will be displayed to two extra decimal places compared to the raw data.

- Categorical variables will be summarized by the number and percentage of subjects within each category. Unless otherwise specified, the percentage will be presented in parentheses to one decimal place. Frequency and percentage values of 0 will be presented as '0' rather than '0 (0)'.
- All summary tables will include the analysis population sample size (i.e., number of subjects) in each treatment group.
- Date variables will be formatted as DDMMMYYYY for presentation.

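### Does the AE duration summary mislead because related events without a stop date get no duration and no planned count?

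*SAP*

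**What the plan says.** SAP section 1.6 lists duration among the adverse event endpoints. The protocol (section 9.1.3.1) says "Duration and time to onset of related AEs will also be presented by treatment group, SOC and PT", and SAP section 2.5.2 repeats the commitment: "For related AEs, the number of days to onset and duration of event will be summarized by treatment group, SOC, and PT".

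SAP section 2.5.2 defines duration as stop date minus start date plus one day. A missing start date is set to the day of treatment. For the other end of the interval the rule is "Missing stop date will not be imputed and therefore no duration will be calculated in these cases".

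On follow-up, protocol section 7.2.5.2.1 states: "Adverse Events (AEs) assessed as related to the treatment or study procedure will be monitored until they have resolved or reached a stable condition". Events not judged related are followed only to the last visit. The items recorded on the eCRF adverse event form include "relationship to the study product, action taken and outcome".

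On presentation, SAP section 2.1.2 sets the default: "Quantitative variables will generally be summarized by the number of subjects, mean, standard deviation, median, minimum, and maximum". It also promises subject listings of all eCRF data and all derived variables. On layouts it says "The formats for the tables, listings, and figures described in this SAP will be provided in a companion document", and later format changes need no SAP amendment. SAP section 2.5 makes all safety summaries descriptive, on observed cases, with no inferential analysis.

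**The concern.** A duration that exists only when the event has ended leaves out events still running. Follow-up of a related event may stop once it is stable, so an unresolved event may never receive a stop date. If the longest events are the ones most likely to lack an end date, the average of the remainder is too low. The maximum is too low as well if an ongoing event outlasts the longest one with a stop date.

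The legible text does not plan to say how many events this affects. The default denominator for a quantitative variable is subjects, whereas the related-TEAE table also counts events, so subtracting one from the other need not give the number without a duration. Nor would it separate an ongoing event from a resolved one whose end date is unknown. Outcome is collected but is not among the breakdowns named in protocol section 9.1.3.1.

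At stake is how a reader interprets the duration of side effects in a dose-ranging trial. If the share left out differed between dose groups, their durations would not be comparable side by side.

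**Working it through.** **1. Is there a figure to reproduce?** No. Neither document states an adverse event duration, an expected number of missing stop dates, or the share of events expected to be ongoing. The visit schedule is redacted. The sizes below are illustrations on assumed inputs.

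**2. Effect on the mean.** Let R be the mean duration of events with a stop date, u the share without one, and E the mean full duration of those left out. Then

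all-event mean = (1 − u)R + uE, so all-event mean − R = u(E − R).

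With R = 14 days (assumed), the difference in days is:

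| u (assumed) | E = 7 | E = 14 | E = 30 | E = 90 |
|---|---|---|---|---|
| 0% | 0 | 0 | 0 | 0 |
| 2% | −0.14 | 0 | +0.32 | +1.52 |
| 5% | −0.35 | 0 | +0.80 | +3.80 |
| 10% | −0.70 | 0 | +1.60 | +7.60 |

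Example: u = 10%, E = 90 gives 0.9 × 14 + 0.1 × 90 = 21.6, which is 7.6 above 14. One event left out of a cell of ten gives the same result: (9 × 14 + 90)/10 = 21.6. The sign depends on whether E exceeds R.

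**3. Effect when an event is left out only because follow-up ended.** Assume exponential durations with mean m days and follow-up of T days after onset. The share without a stop date is exp(−T/m), and the mean of completed events is m − T·exp(−T/m)/(1 − exp(−T/m)).

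| m (assumed) | T (assumed) | Share without stop date | Mean of completed events |
|---|---|---|---|
| 30 | 30 | 36.8% | 12.5 |
| 30 | 90 | 5.0% | 25.3 |
| 30 | 180 | 0.2% | 29.6 |
| 90 | 30 | 71.7% | 14.2 |
| 90 | 90 | 36.8% | 37.6 |
| 90 | 180 | 13.5% | 61.8 |

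Example: m = 30, T = 90 gives exp(−3) = 0.0498, and 30 − 90 × 0.0498/0.9502 = 25.3. The bias is large when follow-up is short relative to the event and nearly vanishes when it is long. Related events have the stronger follow-up rule, to resolution or stability rather than to the last visit, which favours the lower rows of each block.

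**4. What the planned outputs already let a reader recover.**

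- *Every event:* the TEAE incidence tables do not depend on a stop date, so an event without one still counts.
- *Which events lack a duration, and why:* outcome is recorded on the eCRF and duration is a derived variable. Both fall under the listing commitment in SAP section 2.1.2, so the events can be counted and sorted into ongoing and resolved.
- *An approximate count from tables:* the related-TEAE table gives numbers of events by treatment group, SOC and PT. If the duration table shows a number of events, the gap between the two is roughly the number left out, though not the reason. The subject-based default applies only generally, and duration is an event-level quantity.
- *Labels, denominators and footnotes:* these are layout matters, which the SAP assigns to its companion document. That document was not available, so the count cannot be said to be missing from it.

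**The case for a change.** The best argument for a change is that it would be cheap and informative. Outcome is already collected, a footnote needs no SAP amendment, and hand-counting from listings is a poor substitute for a printed number. Someone who sees only the summary table, without the listings, would not know its coverage. A completed-events mean can also be well below the true mean, as the short-follow-up rows above show.

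Much of this is true. The legible text plans no such count, and showing one is good practice that whoever drafts the tables can adopt.

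Two supports are weaker than they look. The form that asks for a resolution date only where applicable (protocol section 7.2.5.2.2) is the AE Clarification Form. It is sent to the safety mailbox only for possible remote spread or hypersensitivity. It is not the eCRF form that feeds the analysis datasets, so it says little about stop dates for related events in general. And it goes too far to say that coverage cannot be known, given the listings. Whether a stable event is given a stop date depends on eCRF completion rules that are not in these documents, so the share left out may be zero.

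The suggested addition would also leave the duration statistics as they are. It would annotate them, in SOC and PT cells that may be sparse with about 60 subjects per dose.

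**Conclusion.** No change to the plan. Declining to invent a stop date is an accepted convention, disclosed in the section where it applies and consistent with observed-cases handling of safety data. What is absent from the legible text is a reporting detail that a table programmer would ordinarily settle in the layouts and that the listings already support.

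The size is unknown. On the assumed inputs (R = 14 days, u from 0 to 10%, E from 7 to 90 days) the difference in the mean runs from −0.7 to +7.6 days. It would be larger if follow-up were short relative to event duration, and negligible if related events nearly all resolve while still being followed. Even at its largest it concerns one descriptive summary: no hypothesis test, efficacy result or TEAE incidence count depends on it. This conclusion rests on the listings being produced as SAP section 2.1.2 promises, with outcome included as protocol section 7.2.5.2.1 requires it to be recorded.
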